Official Title: Improving Physical Activity with Cognitive Impairment

NCT Number: NCT05370118

Document Date: January 29, 2025

1. Study Introduction

The proposed research study examines the feasibility of a telerehabilitation physical activity behavioral (TPAB) 12-week intervention to improve physical activity (i.e., daily steps) for individuals with probable amnesic mild cognitive impairment (MCI) and caregivers. Improving physical activity may promote physical independence, slow the transition from MCI to dementia, and reduce health care costs. This study addresses two significant clinical gaps for amnesic MCI rehabilitation: 1) lack of evidence-based rehabilitation strategies to improve habitual physical activity; and 2) barriers to remotely promote habitual physical activity. We hypothesize that the intervention will be deemed feasible and that individuals with MCI will have greater daily steps after completing the intervention.

2. Background

The prevalence of MCI in older adults is approximately 3-25%,¹⁻³ of which 11-49% will transition to dementia (mainly AD) within two years.^{2, 4} Delaying the transition to dementia by five years is estimated to save \$500,000 per patient.^{5, 6} Addressing modifiable risk factors of dementia, such as physical inactivity, is an approach to delay dementia onset and improve cognitive outcomes and quality of life.^{1, 7-9} Previous reports suggest that more daily steps are linked to better cognition^{1, 7, 10} and less neurodegeneration in individuals with cognitive impairment.^{10, 11} However, there is little literature regarding approaches to increase daily steps in individuals with amnesic MCI (MCI with the domain of memory specifically impaired). Secondly, there is a lack of methods to remotely promote daily steps, which may be especially pertinent for individuals with barriers to participation in standard settings (e.g., those living in rural and underserved areas or those with functional limitations).

A small body of literature has utilized caregivers with physical activity interventions.¹² This will be the first study to our knowledge to engage individuals with probable amnesic MCI and the primary caregiver to facilitate a behavioral intervention targeting improvement in daily steps. Caregivers of individuals with cognitive impairment play a crucial role in daily routines of patients. Involving a primary caregiver has been shown to reduce technology barriers¹³ and improve self-reported physical activity intervention outcomes.^{14, 15} In addition, most caregivers for individuals with cognitive impairment do not engage in regular physical activity.¹⁶ Involving caregivers in the TPAB intervention may improve their physical activity, help them better cope with demands of caring for a loved one, and reduce depression and burnout associated with caregiving.^{15, 17} In addition to the caregiver benefits, approaching physical activity from a dyadic perspective has been suggested as a strategy to maximize effectiveness in individuals with cognitive impairment.¹⁸⁻²⁰

This will be the first study to examine the TPAB intervention that combines health behavior theories/techniques and is remotely delivered to improve daily steps for individuals with probable amnesic MCI and caregivers (patient-caregiver dyads). Prior work has utilized self-reported physical activity,²¹ which suffers from floor effects and recall bias.²²⁻²⁴ A Fitbit (Fitbit Inc., Boston, MA) wearable sensor will be utilized in this study to self-monitor, objectively set goals, and assess goal achievement throughout the

Table 1. Telerehabilitation Physical Activity Behavioral (TPAB) Intervention Outline

Behavior Change Technique	Application	Theoretical Base
Self-monitoring of Behavior (1)	Utilize Fitbit for daily step monitoring	Control Theory
Action Planning (2)	Weekly action planning (goal setting) based on participant step count/identified individual targets	Control Theory
Graded Tasks (3)	Connection to self-monitoring and noted differences with higher/lower step count days	Social Cognitive Theory
Restructuring the Physical (4)/ Social Environment (5)	Discussion of personal barriers/facilitators to exercise and discussion of environmental components that can change	Social Cognitive Theory
Problem-Solving (6)	Discussion of reducing personal barriers and leveraging personal facilitators to increase daily steps	Social Cognitive Theory
Prompts/Cues (7)	Identification of cues that will be useful in self-management of daily steps moving forward and long-term	Operant Conditioning

intervention. The Fitbit wearable sensor is designed specifically to provide visual physical activity feedback through the Fitbit application. The Fitbit sensor will already be connected to a de-identified account created by the research team prior to distribution to study participants. No GPS data is collected. Fitbit use instructions will be provided verbally and in written form. The Fitbit application will provide the participant feedback on the number of steps he/she has taken during daily living activity and progress toward physical activity goals. The research team will monitor the Fitbit physical activity data through the Fitabase platform (see attachment for Fitabase data security and privacy information).

Research-grade accelerometers (ActivPAL, PAL Technologies, Glasgow, UK)²⁵ will be used to objectively measure physical activity (i.e., daily steps) before and after the 12-week intervention.

Enrolled patient-caregiver dyads (individual with probable amnesic mild cognitive impairment and caregiver) will be randomly assigned to either the intervention group (12-week TPAB intervention) or the control group (usual care/no intervention over 12 weeks). Individuals in the TPAB group will participate in virtual 30-minute weekly sessions for 12 weeks with their primary caregiver and the research interventionist ([name]). Established behavior-change techniques will be used in the TPAB intervention (**Table 1**), based largely on the combination of the Social Cognitive Theory, Control Theory, and Operant Conditioning,²⁶ including behavioral techniques, and patient-centered communication (e.g., motivational interviewing).²⁷ The behavior-change techniques are designed to target and improve daily steps. The patient-caregiver dyads in the control group will receive usual care and no intervention (no Fitbit) over the 12 weeks.

3. Research Objectives

Aim 1: Determine the feasibility of the TPAB intervention for individuals with probable amnesic MCI and their primary caregivers by measuring 1) participant retention, 2) attendance, 3) acceptability (Intrinsic Motivation Inventory)²⁸, 3) safety (adverse event tracking), 4) semi-structured interviews.

Aim 2: Examine the preliminary effects of TPAB on physical activity engagement (daily steps) among MCI participants when compared with the control group.

4. Study Population:

Thirty-six individuals with probable amnesic MCI between the ages of 50-85 years old and informal caregivers (19+ years of age) from the Omaha metro and surrounding areas will be recruited to participate in this study. The spectrum of amnesic MCI allows individuals that may or may not be able to give consent and is needed for this study to best reflect individuals with amnesic MCI. If the patient is unable to give consent per research team assessment, a legally authorized representative will be present and sign the consent form and the patient will verbally assent. Additionally, patients will be monitored and withdrawn if they appear to be unduly distressed from participating in the study. Due to anticipated attrition, we plan on recruiting 36 patient-caregiver dyads (18 dyads per group) to meet the necessary 15 dyads per group for statistical purposes. A sample size of 15 patient-caregiver dyads per group will meet our aim to determine a statistically significant change in activity from baseline to post-intervention (13 weeks) with adequate power ($\alpha = .05$, $1-\beta = .8$) ability to detect an effect size of approximately $d = 1.06$.

5. Inclusion/Exclusion Criteria

Inclusion criteria for participants with probable amnesic MCI are: 1) 50-85 years old, 2) memory impairment as demonstrated with deficits in the memory domain scores on the Montreal Cognitive Assessment (MoCA), 3) a score of 18-24 on the MoCA indicating possible MCI,²⁹ 5) not currently categorized as “Active” on the Rapid Assessment of Physical Activity,³⁰ 6) have a primary caregiver willing to participate in physical activity and assist the patient with participation in the study. Inclusion criteria for both the patient and caregiver include: 1) self-reported household ambulator, 2) on stable doses of medication at least for the previous 30 days at baseline, 3) have a computer/wireless device with Internet access, 4) English-speaking. Caregiver must additionally score 24 or higher on the Mini-Mental Status Exam (MMSE) indicating no impairment to be included in the study³¹ and be 19+ years of age. If the caregiver does not meet this requirement the patient will be asked if there is another caregiver willing to participate in the study.

Exclusion criteria for the patients and caregivers are: 1) limitations due to disability, illness, or pain that may affect the patient’s walking safety during the study, 2) unstable heart conditions (e.g., unstable angina, acute pericarditis) 3) uncontrolled hypertension in the last six months, 4) known neurological diseases. All medical criteria will be assessed via self-report.

6. Subject Recruitment:

Investigators will use the UNMC Mind Brain Health Registry (398-15) and distribute fliers at locations that treat individuals with amnesic MCI. Participants on the registry who are care partners of individuals with MCI or individuals with MCI will be contacted. Fliers may also be distributed on social media platforms (e.g., Facebook, Twitter). Fliers will be distributed to share basic study information. Participants will voluntarily identify if interested in this study and will communicate (e.g. call, email) with [name] from the contact information provided on the fliers. Potential participants will be pre-screened via

a standardized phone screen that includes an exercise medical clearance questionnaire (PAR-Q+). If the results of the PAR-Q+ indicate consultation with the individual's primary care provider prior to starting the physical activity intervention proposed in this study, then the individual will be asked for PCP contact information and the research team will receive PCP medical clearance prior to consent and baseline testing. During the consent process, individuals with probable amnesic MCI will be asked a series of questions (Capacity Screening Questions attachment) to determine if he/she has the capacity to consent. If the individual with probable amnesic MCI can answer the capacity screening questions it will be determined they have the ability to consent to the study. If the individual with probable amnesic MCI, is unable to answer the capacity screening questions then the individual's LAR will be contacted prior to completing the consent process. At the initial visit, the remaining screening will occur for the patient: 3) a score of 18-24 on the Montreal Cognitive Assessment indicating possible MCI,²⁹ 5) not currently categorized as "Active" on the Rapid Assessment of Physical Activity, and the caregiver: score 24 or higher on the Mini-Mental Status exam.

Additionally, potential research participants will be recruited by snowball sampling, enrolled participants referring the research team to others that may qualify.

7. Risks

Our patient population (aged 50-85 years) and the possibility of older caregivers (19+) may include individuals that have medically complex conditions that still meet inclusion/exclusion criteria. To improve the safety of all participants in TPAB intervention, the intervention includes discussion about safety with physical activity throughout.

In the TPAB intervention group, we anticipate the risk of muscle soreness and exposure to falls due to increased exposure to walking (dependent on the efficacy of TPAB intervention). Falls are defined as "inadvertently coming to rest on the ground, floor or other lower level, excluding intentional change in position."³² Fall risk will be mitigated in the study by discussing walking safety and determining appropriate stepping goals throughout the TPAB intervention. The occurrence of falls will be recorded for the patient-caregiver dyads that are in the TPAB intervention group and the control group at all outcome testing sessions and TPAB intervention sessions. In addition, the control group will be contacted each week to determine if any falls or other adverse events have occurred. As such, study progress and adverse events (falls or other adverse events) will be reviewed on a case-by-case basis and the IRB will be notified. If the number of injurious falls for the TPAB intervention group exceeds that of the control group by 5 (7% of enrollment) at any time, the study will be suspended until an evaluation of study relatedness for each incidence is performed.

Also, some questions may make subjects feel uncomfortable. There is a rare but significant risk of loss of confidentiality. There may also be risks that are unknown at this time.

8. Benefits

Individuals with mild cognitive impairment in the TPAB intervention group may improve physical activity (daily steps). Some possible benefits of improving physical activity in individuals with MCI include greater independence, better cognitive performance, and greater quality of life.^{1, 7-9}

Caregivers that are in the TPAB intervention group may also improve physical activity. Benefits associated with increased physical activity for caregivers could include decreased symptoms of depression and less caregiver burnout.^{15, 17}

No benefits are anticipated for individuals in the control group.

The success of this remotely administered TPAB intervention can provide data for a larger-scale efficacy study that may ultimately advance reach to rural and underserved areas.

9. Assessment of Potential Risks and Benefits

The study is considered minimal risk since all data collection will occur in non-invasive methods (e.g., questionnaires, audio recordings, and thigh worn activity monitor). The intervention poses no more than minimal risk. The individuals in the intervention group will likely engage in more physical activity (dependent on the efficacy of the intervention) than the control group. The intervention is targeted at improving daily steps and does not specifically target an intensity (e.g., moderate intensity). Considering walking is an activity all our enrolled participants do every day this study poses no more than minimal risk. Common risks associated with walking include mild muscle soreness and falls. The benefits outlined in section 8 outline the moderate impact of the intervention on patients and caregivers. These outcomes can drive future larger clinical trials examining the TPAB intervention and ultimately can make substantial positive impacts on individuals with cognitive impairment and their caregivers.

10. Study Duration

The study duration will be approximately one year as specified by the grant-awarding agency.

11. Participant Duration

Both groups will undergo testing at baseline (before randomization to TPAB intervention or control group) and post-intervention. Consent and baseline testing will be conducted entirely in person (e.g. home setting). Post-testing will at a minimum involve cognitive testing (Trails A & B) done in person with an option for remaining outcomes completed in their preferred setting (e.g., home setting, via phone, or video call (Creighton's Zoom platform)). Research personnel will be present to assist with any questions or issues with questionnaire completion. Phone and video outcomes testing sessions will not be recorded except for the semi-structured interviews for individuals that underwent the intervention. All study personnel will act as mandatory reporters, if events or circumstances are witnessed during baseline, post, or intervention sessions. If

undergraduate students assisting with the research witness events, they deem reportable, they will discuss with the PI ([name]) to determine what agency should receive the report, if necessary. The testing procedures are detailed below and will take approximately 2 hours to complete at each testing time point (baseline and post-intervention). The TPAB intervention will involve weekly 30-minute sessions with [name] for 12 weeks. The details of information covered during the TPAB intervention sessions are outlined in the Intervention Checklist attachment. For the TPAB intervention group, all participants (patients and caregivers) will be provided a Fitbit. Directions on how to interact with the Fitbit app will be discussed during the first intervention session and are detailed in the Patient-Workbook attachment. It is expected that participants will return the provided Fitbit at the end of their study participation. Due to the 7-day activity monitor data collection prior to and following the 12-week TPAB intervention, participants will be enrolled in the study for approximately 14 weeks.

To assess Aim 1, we will measure retention, attendance, acceptability, safety, and qualitative feasibility perspectives. Based upon previous research, we expect to retain at least 85%³³ and attendance of at least 80%³⁴ to deem the study a success. The TPAB intervention will be regarded as acceptable with a mean of >5.0 (null value)³⁵ on the Intrinsic Motivation Inventory – Interest / Enjoyment Subscale.²⁸ The number of adverse events in the TPAB intervention group will be similar to that of the control group and will not exceed five adverse events related to the TPAB intervention. Finally, qualitative feasibility data will be gathered via audio recorded semi-structured interviews.

To assess Aim 2, we will measure daily steps at baseline and post-intervention. Daily steps will be measured across seven days at each time point (from the activPAL). Refer to ActivPAL instructions attachment for more details about activity monitor placement. Previous work has shown individuals with MCI can reliably and feasibly wear activity monitors.^{7, 36, 37} We hypothesize that the TPAB intervention group will make significant gains in daily steps from baseline to post-intervention compared to the control group.

Baseline descriptive measures will include demographics (age, sex, education level), and anthropometrics (height, weight, BMI). Patient-caregiver dyads will additionally be assessed on the following outcome measures to determine associations with Aim 1 and Aim 2 outcomes: comorbidities (Functional Comorbidity Assessment³⁸) self-reported mobility (International Physical Activity Questionnaire,³⁹ Physical Activity Scale for Elderly,⁴⁰ PROMIS HAQ⁴¹), global cognitive function (Montreal Cognitive Assessment²⁹ and Mini-Mental Status Exam³¹), perceptual-motor function (Trails Making Test A⁴²), executive function (Trails Making Test B⁴²), depression (Geriatric Depression Scale⁴³), quality of life (Logsdon QOL-AD Scale^{44, 45} and Short Form-36⁴⁶), and caregiver burden (Caregiver Burden Inventory^{47, 48}). Theory-based determinates⁴⁹ of knowledge (Apathy Scale^{50, 51}), self-efficacy (Self Efficacy for Exercise Scale⁵², Self-Efficacy of Managing Chronic Disease⁵³), outcome expectations (semi-structured interview), goals (semi-structured interview, % weekly goal attainment), and perceived facilitators (Multidimensional Scale of Perceived Social Support⁵⁴) will be assessed to explore the TPAB intervention behavioral targets. Collection methods for the above-stated outcomes are outlined in Table 2.

12. Compensation

Patients and caregivers will each be compensated with a \$30 gift card for each testing session (2 testing sessions per participant). Compensation will be provided at the end of each testing session. This gives the opportunity for each participant to be compensated \$60 total in amazon gift cards (\$120 total for the patient-caregiver dyad). Additionally, all participants that complete the post-testing will be given a Fitbit at the end of the study for both the intervention and control groups.

Table 2. Data Collection Source Information

Data Collection Method	Outcomes
Questionnaires (electronically completed via tablet or laptop)	Acceptability (IMI) Comorbidities (Comorbidities Index) Mobility (IPAQ) Depression (GDS) Quality of Life (QOL-AD & SF-36) Caregiver burden (Caregiver Burden Inventory) Determinates of knowledge (Apathy Scale) Self-efficacy (SEE & self-efficacy for managing chronic disease) Perceived facilitators (MSPSS) Goals/Outcome expectations (PSFS, located on page 8 of the Patient-Workbook Attachment)
Participant Self-Reported	Demographics Frequency of Fitbit interaction
Semi-structured interview (TPAB intervention group participants only)	Qualitative feasibility of TPAB intervention (identification of themes across participants)
Researcher reported	Retention (keep track of subject drop out) Attendance (keep track of number of TPAB sessions attended) Safety (Weekly Health Problem Tracking Sheet) Blood Pressure/Heart Rate
ActivPAL (research grade activity monitor)	Daily steps
Fitbit/Fitabase	Weekly step goal attainment
Tests	Global Cognitive Function (MoCA & MMSE) Perceptual-motor function (Trails A Test) Executive Function (Trails B Test)

13. Confidentiality and Privacy

We will keep all research records that contain identifiable health information, confidential to the extent allowed by law. Paper records will be kept in a locked filing cabinet in [name] office at Creighton University while electronic records will be stored on password-protected computers and user-restricted drives. A description of this clinical trial and a summary of the results will be available on <http://www.clinicaltrials.gov>, as required by U.S. law. Additionally, the research team and appropriate governing agencies will have access to the data. Each patient and caregiver will be assigned a study identifier (e.g. MCIBC_01) that will be associated with all research data. Participants' identifiable information (e.g. name, address, phone number) will be stored separately from research data and kept per contract of the funding agency. Deidentified research data will be securely kept indefinitely.

14. Informed Consent Process

We will e-mail or mail potential participants the consent form prior to the first study visit (baseline). This will allow participants ample time to review forms in advance should they desire. At the consent meeting, before reviewing the consent forms, patients and caregivers will be assessed to determine if they meet the remaining inclusion and exclusion criteria. If the remaining criteria are met, patients and caregivers will complete individual/separate consent forms. If a study investigator is unable to attend the baseline testing, remote consent will be conducted via HIPAA Zoom (voice call will be used if video conference is not possible) with the study investigator and potential participants. The consent will be electronically signed via DocuSign. This virtual consent process was previously approved in protocol 2003401. In this circumstance, student investigators will conduct the remaining components of the baseline testing session. During the consent process, the research personnel will review the purpose of the project, details of study participation, potential benefits/risks, and compensation. During this process, any questions will be answered regarding the study. It will be made verbally known that participation in this research is voluntary. If the potential participant chooses not to participate, it will not affect their relationship with the investigative team. The participant is free to withdraw consent and discontinue participation at any time without prejudice. During the consent process, individuals with probable amnesic MCI will be asked a series of questions (Capacity Screening Questions attachment) to determine if he/she has the capacity to consent. If the individual with probable amnesic MCI is able to answer the capacity screening questions it will be determined, they have the ability to consent to the study. If the individual with probable amnesic MCI, is unable to answer the capacity screening questions then the individual's LAR will be contacted prior to completing the consent process. If a legally authorized representative (LAR) is necessary, the LAR will sign the consent form and the patient will verbally assent for enrollment of the study to occur. The target population for this study is individuals with probable amnesic MCI as clinically determined by cognitive testing and will not include individuals with severe cognitive deficits (e.g., dementia, Alzheimer's disease). After signing consent forms patients and caregivers will be formally entered into the study and study-related questionnaires will follow (baseline testing). Copies of the signed consent forms will be provided to all participants. Vulnerable populations such as children, prisoners, non-English speakers, and severe cognitive impairment will not be enrolled in this study.

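### The patient's medical eligibility rests on self-report by people selected for memory impairment, no corroboration is stated, and primary care clearance is reached only if the PAR-Q+ answers call for it

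*Combined protocol and SAP*

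**What the plan says.** Section 5 opens its list of exclusions with "Exclusion criteria for the patients and caregivers are". The list covers limits on walking safety, unstable heart conditions, "uncontrolled hypertension in the last six months" and known neurological disease. It closes with the rule on source: "All medical criteria will be assessed via self-report". Among the inclusion criteria, patient and caregiver must each be "on stable doses of medication at least for the previous 30 days at baseline".

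Patients qualify through memory-domain deficits and a total score of 18-24 on the MoCA (Section 5). Section 4 accepts that some will be unable to consent and provides for an LAR. Each patient must also "have a primary caregiver willing to participate in physical activity and assist the patient with participation in the study", and that caregiver must score at least 24 on the MMSE.

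Section 6 places the PAR-Q+ in a phone pre-screen. If it points to consultation, the research team obtains clearance from the primary care provider before consent and baseline testing. Section 14 has patients and caregivers checked against the remaining criteria at the consent meeting, before the forms are reviewed. Section 15 has the HIPAA form signed once phone-screen eligibility is settled.

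**The concern.** Two of the criteria look back over a fixed period: 30 days for medication and six months for hypertension. The others depend on the respondent knowing and reporting a diagnosis or limitation. These are the answers on which a person with a memory deficit is least dependable, and the plan names no second source for them.

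Two things are at stake. The first is safety. Section 7 expects more exposure to falls in the intervention group and accepts that participants may be medically complex. The safety limits are small counts: an excess of five injurious falls (Section 7) and five adverse events related to the intervention (Section 11). The second is who is studied. An undeclared neurological disease would put patients into the probable amnesic MCI group whom the protocol means to leave out.

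**Working it through.** The plan has no figure on this point to reproduce, so the main check follows the order of screening steps.

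1. **Phone screen (Section 6).** The PAR-Q+ is completed. The respondent is not named. Registry contact may be with a care partner or with the person with MCI, so the informant could differ between dyads.
2. **Primary care clearance (Section 6).** Sought only if the PAR-Q+ indicates it. A condition that is not reported produces no trigger, and the provider is not asked.
3. **HIPAA authorization (Section 15).** Signed after phone-screen eligibility.
4. **Remaining criteria (Sections 6 and 14).** Section 6 names what is left for the initial visit: the patient's MoCA and Rapid Assessment of Physical Activity, and the caregiver's MMSE. The medical criteria are not in that list, so nothing as written brings them up again.
5. **Capacity questions (Sections 6 and 14).** Asked during the consent process. A patient who cannot answer them may already have given the medical history by phone. The LAR is then contacted for consent, but no one is told to go back over those answers.
6. **Other medical information.** The comorbidity questionnaire is part of study testing, which Section 14 places after consent. Blood pressure and heart rate appear in Table 2 as researcher-reported, with no timing and no link to an eligibility criterion.

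A condition the patient forgets can therefore pass every stated step.

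**Illustration of size (all rates assumed).** Let p be the share of screened patients with an excluding condition, s the share of those that self-report detects, and c the share of missed cases that confirmation catches. The proportion of enrolled patients who are ineligible is

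q = p(1 - s)(1 - c) / [1 - p + p(1 - s)(1 - c)],

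and the expected number among 36 is 36q.

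- Low end, p = 0.05, s = 0.95, c = 0: 0.0025 / 0.9525 = 0.0026; 36q = 0.09.
- High end, p = 0.20, s = 0.70, c = 0: 0.06 / 0.86 = 0.0698; 36q = 2.51.
- Same two cases with c = 0.5: 0.00125 / 0.95125 = 0.0013, giving 0.05; and 0.03 / 0.83 = 0.0361, giving 1.30.

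The range reflects the chosen inputs. It is not an estimate for this trial.

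**The case against.** Self-reported screening is a disclosed choice in a 36-dyad feasibility study that Section 9 classes as minimal risk. The activity is everyday walking with no intensity target. Adverse events are tracked in both groups, severe cognitive deficits are excluded, and a patient without capacity has an LAR. No effect on power, error rate or the Aim 2 estimate can be shown, and any ineligible patients would be randomized to either group. All of this stands. It limits the weight of the point, but none of it supplies a check on the patient's answers.

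Three stronger readings are tempting and should not be adopted.

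- A reader might infer that all exercise clearance depends on the word of memory-impaired people. Section 6 has a provider step, and only its trigger is a questionnaire. The self-report rule also covers caregivers.
- A reader might infer that caregivers are kept out of screening. The document is silent on who answers the phone screen, and silence does not exclude them.
- A reader might infer that the protocol contradicts itself, because Section 2 says self-report "suffers from floor effects and recall bias". That remark concerns self-reported physical activity as a measurement. It does not address reporting a diagnosis, and it is not relied on here.

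A practical objection also stands: the phone screen comes before both the caregiver's MMSE and the HIPAA form, so it is the wrong place for confirmation.

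**Conclusion.** The point holds in a limited form. The plan states self-report as the source of the patient's medical criteria, selects those patients for memory impairment, and states no corroboration. The conditional primary care step does not close the gap, because an unreported condition does not set it off.

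The rule applies to all 36 patients, but the number wrongly enrolled cannot be derived from the document. The illustrative 0.1 to 2.5 rests wholly on assumed prevalence (5% to 20%) and assumed detection by self-report (70% to 95%). The finding is a gap in the screening procedure with an inexpensive remedy. It does not show that ineligible patients have entered or that the sample size calculation is affected.

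**What to change.** Amend Section 5 along these lines: the patient's self-reported medical criteria, medication stability and PAR-Q+ answers are confirmed at the pre-consent eligibility check in Section 14, after HIPAA authorization, with the study caregiver (once an MMSE score of at least 24 is established) or with the LAR. Any disagreement is resolved through the primary care contact in Section 6 before consent. Where the need for an LAR emerges only from the capacity questions, the LAR's confirmation should come before the LAR signs. Section 6 should also state who answers the phone screen. The criteria themselves do not change.

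The cost is a few extra minutes at a visit already planned, and an occasional primary care query that delays consent. No new visit or staff is needed. The team should check that the HIPAA form covers discussing the patient's history with the caregiver, since its wording is not in the document.

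If enrolment has already closed, report the uncorroborated self-report as a limitation and carry the rule into the larger study that Section 8 foresees.
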